10.1.3 Estimand Framework

Population

The target population is participants with IBS-C, ages 7-17 years old, satisfying the inclusion and exclusion criteria as specified in Sections 5.1 and 5.2 of the protocol (Version June-2020), respectively.

The analysis population is mITT as discussed in Section 6.3.

Variable

The variable is the primary efficacy endpoint defined in Section 10.1, which is 6/12 weeks APS (abdominal pain and SBM) + 2 responder as derived from twice daily responses in eDiary (morning and evening). SBM is derived based on responses for BM and rescue medication in the eDiary twice daily (morning and evening). Abdominal pain score is also derived based on responses in the eDiary twice daily for abdominal pain.

Accounting for Intercurrent Events in the Primary Efficacy Analyses

The following intercurrent events are considered for the primary efficacy analyses. All the intercurrent events are handled based on the composite strategy.

- The BMs for the participants who took a laxative, enema, or suppository on the calendar day of the BM or the calendar day before the BM will not be considered as SBMs for the analysis.
- Participants who discontinue prematurely during but prior to the completion of the double-blind Study Intervention Period will have their eDiary data included up to the morning diary following the last dose date for primary endpoint. The early discontinued participants will be considered non-responders for the following weeks for primary endpoint.
- eDiary responses following the onset of dose de-escalation will not be included. The participants with dose de-escalation will be considered non-responders for the subsequent study intervention weeks (after the onset of dose de-escalation) for the primary endpoint based on the randomized study intervention group.
- A participant has to have at least 4 completed diary days per study intervention week to be considered a responder for that week and otherwise, the participant will be considered non-responder for that week. A completed diary day is a day in which both morning and evening eDiary entries are filled out by a study participant.

Population-level Summary

The population-level summary for the primary endpoint is the proportion of participants satisfying the APS + 2 responder criteria for at least 6 out of 12 weeks during the study intervention period for each linaclotide dose.

A Bayesian analysis will be performed for the primary efficacy endpoint using adult IBS-C data (borrowed from studies MCP-103-202, MCP-103-303, and LIN-MD-31) to inform the prior distribution of response in pediatric IBS-C patients. The 2.5 percentile of posterior distribution for the APS + 2 responder rate for linaclotide 145 µg or 290 µg will be compared separately with the pooled placebo APS + 2 responder rate and with the upper limit of 95% CI of the pooled placebo responder rate from contributing adult studies as discussed in Section 10.1.1.

10.2 Secondary Efficacy Endpoints

The secondary efficacy endpoints are as follows:

- Change from baseline in 12-week SBM frequency rate (SBMs/week) during the study intervention period
- Change from baseline in 12-week abdominal pain during the study intervention period
- Change from baseline in 12-week stool consistency during the study intervention period
- 6/12 weeks SBM + 2 responder
- 6/12 weeks abdominal pain responder

Change From Baseline in 12-Week SBM Frequency Rate During the Study Intervention Period

Assessments of BM characteristics that determine occurrences of SBM (ie, BM frequency and RM use) will be measured by using the eDiary completed twice daily (morning and evening) on the eDiary device.

The 12-week SBM frequency rate (SBMs/week) during the study intervention period will be derived based on total number of SBMs a participant reported during this period in the morning and evening assessments on the eDiary. The details of the derivation of SBM frequency rate are provided in Section 16.3.4.

Change From Baseline in 12-Week Abdominal Pain During the Study Intervention Period

Abdominal pain will be measured twice daily, once in the morning and once in the evening eDiary, using a 5-point scale. The 12-week abdominal pain score during the study intervention

period will be derived for each participant based on the reported abdominal pain scores in morning and evening eDiary assessments during this period. The details of the derivation of abdominal pain score are provided in Section 16.3.5.

Change From Baseline in 12-Week Stool Consistency During the Study Intervention Period

Stool consistency will be measured twice daily, once in the morning and once in the evening eDiary, using the 7-point ordinal p-BSFS for each BM. The 12-week stool consistency score during the study intervention period will be derived based on the responses in morning and evening eDiary assessments during this period. If the participant has no SBM during the baseline period, the stool consistency (p-BSFS score) during the baseline period will be missing and the participant will be excluded from the change from baseline analysis for this secondary endpoint. The details of the derivation of stool consistency are provided in Section 16.3.6.

6/12 Weeks SBM + 2 Responder

A 6/12 weeks SBM + 2 responder is a participant who meets the weekly SBM + 2 responder criteria for at least 6 out of the 12 weeks of the study intervention period. A weekly SBM + 2 responder is a participant who had an increase of at least 2 in the SBM weekly rate from baseline during that study intervention week. A participant has to have at least 4 completed diary days in analysis week to be considered as responder for that week and otherwise, will be considered as non-responder for that analysis week.

6/12 Weeks Abdominal Pain Responder

A 6/12 weeks abdominal pain responder is a participant who meets the weekly abdominal pain responder criteria for at least 6 out of the 12 weeks of the study intervention period. A weekly abdominal pain responder is a participant who had a decrease of at least 30% in the mean abdominal pain score from baseline during that study intervention week. A participant has to have at least 4 completed diary days in analysis week to be considered as responder for that week and otherwise, will be considered as non-responder for that analysis week.

10.2.1 Main Analysis Approach

Descriptive statistics for continuous secondary endpoints in terms of mean, median, standard deviation, standard error of mean, minimum, and maximum will be provided by study intervention group. For responder endpoints, counts and percentages will be provided by study intervention group.

10.2.2 Supplemental Analysis

Weekly responder rates (counts and percentages) will be provided separately for abdominal pain weekly responders and SBM+2 weekly responders by study intervention group. By-week summary (mean, median, SD, standard error of mean, minimum, and maximum) will be provided for change from baseline in SBM frequency rate, abdominal pain, and stool consistency separately.

The descriptive statistics (mean, median, SD, standard error of mean, minimum, and maximum for continuous endpoints and counts and percentages for responder endpoints) will also be provided by study intervention sequence incorporating efficacy responses following onset of dose-de-escalation for secondary efficacy endpoints.

10.3 Other Efficacy Endpoints

The other efficacy endpoints are as follows:

- 6/12 weeks APS + 1 responder
- 9/12 weeks SBM + 2 responder
- 9/12 weeks abdominal pain (combined daytime and nighttime symptoms) responder
- 9/12 weeks APS + 2 responder
- Proportion of participants with SBMs within 24 hours of first dose of study intervention
- Change from baseline in 12-week straining during the study intervention period
- Change from baseline in 12-week abdominal pain (daytime symptoms and nighttime symptoms separately) during the study intervention period
- Change from baseline in 12-week percent of abdominal pain (combined daytime and nighttime symptoms)-free days during the study intervention period
- Change from baseline in 12-week bloating (daytime, nighttime, and combined symptoms) during the study intervention period
- Change from baseline in 12-week CSBM frequency rate (CSBMs/week) during the study intervention period
- Proportion of participants who no longer fulfill Rome III criteria for IBS-C at the end of the study intervention period
- Proportion of participants with each individual item score for the participant-completed global change items (pooping problems, tummy problems, and tummy pain) and global severity items (pooping problems, tummy problems, and tummy pain) at each week during the study intervention period
- Proportion of participants with each individual item score for the observer-completed global change item and the global severity item at each week during the study intervention period (collected for age group of 7-11 years only)

6/12 Weeks APS + 1 Responder

A 6/12 weeks APS + 1 responder is a participant that meets the weekly APS + 1 responder criteria for at least 6 out of the 12 weeks of the intervention period. A weekly APS +1 responder is a participant who has an increase of at least 1 in the SBM weekly rate from baseline, AND a decrease of at least 30% in the mean abdominal pain score (combination daytime and nighttime) from baseline, during that study intervention week. This responder endpoint will be derived similar to the primary endpoint as discussed in Section 10.1. The proportion of participants

satisfying responder criteria for at least 6 out of 12 weeks during the study intervention period will be presented by study intervention group.

9/12 Weeks SBM + 2 Responder

A 9/12 weeks SBM + 2 responder is a participant that meets the weekly SBM + 2 responder criteria for at least 9 out of the 12 weeks of the intervention period. A weekly SBM +2 responder is a participant who has an increase of at least 2 in the SBM weekly rate from baseline during that study intervention week. A participant has to have at least 4 completed diary days in analysis week to be considered as responder for that week and otherwise, will be considered as non-responder for that analysis week.

The proportion of participants satisfying responder criteria for at least 9 out of 12 weeks during the study intervention period will be presented by study intervention group.

9/12 Weeks Abdominal Pain (Combined Daytime and Nighttime Symptoms) Responder

A 9/12 weeks abdominal pain responder is a participant who meets the weekly abdominal pain responder criteria for at least 9 out of the 12 weeks of the study intervention period. A weekly abdominal pain responder is a participant who had a decrease of at least 30% in the mean abdominal pain score from baseline during that study intervention week. A participant has to have at least 4 completed diary days in analysis week to be considered as responder for that week and otherwise, will be considered as non-responder for that analysis week.

The proportion of participants satisfying responder criteria for at least 9 out of 12 weeks during the study intervention period will be presented by study intervention group.

9/12 Weeks APS + 2 Responder

A 9/12 weeks APS + 2 responder is a participant that meets the weekly APS + 2 responder criteria for at least 9 out of the 12 weeks of the intervention period. A weekly APS +2 responder is a participant who has an increase of at least 2 in the SBM weekly rate from baseline, AND a decrease of at least 30% in the mean abdominal pain score (combination daytime and nighttime) from baseline, during that study intervention week. This responder endpoint will be derived similar to the primary endpoint as discussed in Section 10.1. The proportion of participants satisfying responder criteria for at least 9 out of 12 weeks during the study intervention period will be presented by study intervention group.

Proportion of Participants with an SBM within 24 Hours of First Dose of Study Intervention

A participant is a 24-hour responder if the participant has at least 1 SBM within 24 hours of first dosing of study intervention. Any SBM reported in the evening diary on randomization day and in the morning diary at the day after first dose date (i.e., Day 2) will be considered a SBM within 24 hours. The proportion of participants satisfying responder criteria will be presented by study intervention group.

Change From Baseline in Other Efficacy Endpoints Related to Bowel Habits and Abdominal Symptoms

The derivations of straining, abdominal pain (daytime and nighttime), bloating (daytime, nighttime, and combined daytime and nighttime symptoms), and CSBM frequency rates (CSBMs/week) during the Study Intervention Period are discussed in Section 16.3.7, Section 16.3.5, Section 16.3.8, and Section 16.3.4, respectively.

Descriptive statistics (mean, median, SD, standard error of mean, minimum, and maximum) will be presented by study intervention group.

Change from Baseline in 12-week Percent of Abdominal Pain (Combined Daytime and Nighttime Symptoms)-Free Days During Study Intervention Period

The percent of abdominal pain-free days during the analysis period will be derived as the number of days with abdominal pain (combined daytime and nighttime symptoms) scores of 0 divided by the total number of days with non-missing abdominal pain scores in the period (baseline or study intervention period) multiplied by 100. If a participant has reported abdominal pain score (any non-zero value from 1 to 4) in at least one eDiary (morning or evening) on a specific day during the analysis period, that day will not be counted as abdominal pain-free day during that analysis period.

Descriptive statistics (mean, median, SD, standard error of mean, minimum, and maximum) will be presented by study intervention group.

Proportion of Participants Who No Longer Fulfill Rome III Criteria for IBS-C at the End of the Study Intervention Period

The details of the derivation of this endpoint are discussed in Section 16.3.9. The proportion of participants who no longer fulfill Rome III criteria for IBS-C at the end of the study intervention period will be presented by study intervention group.

Participant-Completed Global Change Items and Global Severity Items at Each Week During Study Intervention Period

The details of participant-completed global change item scores and global severity item scores are discussed in Section 16.3.10. For each of the participant-completed global change items (pooping problems, tummy problems, and tummy pain) and global severity items (pooping problems, tummy problems, and tummy pain), counts and percentages for each category within each individual item will be provided by study intervention group at each week during the study intervention period.

Observer-Completed Global Change Item and Global Severity Item at Each Week During Study Intervention Period

The observer-completed global change item and global severity item will be assessed on a weekly basis in the eDiary, for the 7 - 11 years of age group only as discussed in Section 16.3.11. Counts and percentages of the global change item and the global severity item will be provided by study intervention group at each week during the study intervention period.

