#### **Bowel Movement Frequency**

- Morning eDiary

From bedtime last night until now, how many times did you poop (and poop came out)?

- Enter number of times

- Evening eDiary

From when you got up this morning until now, how many times did you poop (and poop came out)?

- Enter number of times

If response is > 0 BMs, then the participant answers the following question for each BM reported:

When did you poop today?

- In the morning (from when you woke up until lunch)
- In the afternoon (from lunch until dinner)
- In the evening (from dinner until bedtime)

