### 10.10.3. Randomization (Visit 3, Day 1)

Participants' eligibility to enter the Study Intervention Period must be confirmed prior to randomization by review of inclusion and exclusion criteria, including a fecal impaction assessment, adherence to instructions regarding the use of rescue medication and prohibited medications, meeting eligibility criteria captured in the eDiary device, including full compliance with eDiary on at least 10 of the 14 days immediately preceding Visit 3. Participants will be required to complete the eDiary in the clinic for the time period up to immediately prior to randomization. The study coordinator will obtain the eDiary eligibility report to determine eDiary-related eligibility to be randomized. Once the participant's randomization eligibility is confirmed based on the eDiary eligibility report and other inclusion and exclusion criteria, the IWRS will randomize the participant. Study personnel will review the study procedures with participants and instruct them to resume eDiary entries later on the day of randomization.

Randomization will occur on the first day of the Study Intervention Period. Based on randomization, participants will receive placebo (FC participants) or linaclotide (FC and IBS-C participants). Participants will complete at least 12 weeks of intervention during the double-blind Study Intervention Period (ie, Study Intervention Period).

During the Randomization Visit (Visit 3), the following procedures will be performed:

- Review inclusion and exclusion criteria, including review of eDiary-related criteria
- IWRS verification
- Perform a fecal impaction assessment after eDiary eligibility is confirmed and prior to randomization. If fecal impaction is present, the participant will not be eligible for the study.
- Obtain weight; temperature (oral, rectal, or tympanic) and respiratory rate; and postural vital signs (supine and standing systolic and diastolic BP and pulse rate).
- Obtain clinical laboratory tests consisting of clinical chemistry, hematology, and urinalysis. All laboratory tests requiring blood draws should be collected at the same time
- Obtain a urine pregnancy test for female participants of childbearing potential. A negative urine pregnancy test is required prior to receiving study intervention
- Review any AEs occurring since the last visit
- Review concomitant medications
- Review eDiary completion, including the Clinic eDiary

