- Ensure participants have refrained from using rescue medicine on the prior calendar day and on the day of the Randomization (Visit 3) until the time of the clinic visit.
- Remind participants not to use rescue medicine for the remainder of the day and on the next calendar day after the Randomization Visit
- Run the eDiary Eligibility Report to confirm that the participant can be randomized.
- Review use of protocol-permitted rescue medication dispensed in IWRS where applicable. Participants may choose a different protocol-permitted rescue medication at any visit, where available. Additional protocol-permitted rescue medications may be dispensed as needed at any visit.
- Prior to dosing, the investigator or appropriate site staff member will assess Rome IV criteria for Child/Adolescent IBS and/or FC. Assessment result will be captured in the eCRF. Eligibility for the study is not based on this assessment
- Contact the IWRS to obtain the study intervention (bottle number) to be dispensed to the participant based on randomization
- Administer the first dose of study intervention after completion of all Visit 3 assessments and after confirming the participant has fasted for at least 2 hours. Participants may resume eating 30 minutes after receiving their first dose of study intervention at the study site

- Dispense assigned study intervention for this study after the first dose has been administered. Provide study intervention reconstitution instructions for sprinkles to participants and caregivers for participants who may not be able to swallow capsules (Section 10.8)
- Record the date and time the first dose was administered
- Remind participant and caregiver to bring the bottle(s) of the study intervention and rescue medication to the next visit

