16.2 Visit Time Windows for Efficacy Analyses

Table 16-2 below presents the analysis weeks assigned for the efficacy analysis of the participant daily diary data related to BM and/or abdominal symptom characteristics. These analysis weeks

will be used in the calculations for all week-based endpoints (eg, SBM weekly frequency rate, etc.).

Table 16-2. Analysis Time Windows for Efficacy Analysis - Daily Questions

Period	Analysis Week	Begins ^a	Ends ^a
Preintervention (Baseline ^b)	Week -2	Day -14	Day -8
	Week -1	Day -7	Day 1, time of randomization
Intervention	Week 1	Day 1, time after randomization	Day 7
	Week 2	Day 8	Day 14
	Week 3	Day 15	Day 21
	Week 4	Day 22	Day 28
	Week 5	Day 29	Day 35
	Week 6	Day 36	Day 42
	Week 7	Day 43	Day 49
	Week 8	Day 50	Day 56
	Week 9	Day 57	Day 63
	Week 10	Day 64	Day 70
	Week 11	Day 71	Day 77
Week 12	Day 78	Day of last dose +1	
Post-intervention	Post-intervention	Day of last dose + 1	Day of end of study visit

Note: On randomization day, if participant already completed morning diary, at the clinic visit, participants fill out a clinic diary and the assessments in the clinic diary will be part of the Preintervention Period. Morning diary assessments on randomization day will also be part of Preintervention Period. eDiary assessments in evening diary on the day of randomization will be part of the Intervention Period. eDiary assessments in morning diary at the day after the last dose day will be considered as assessments in the Intervention Period.

- a. Relative to the date of randomization; Day 1 the day of randomization.
- b. Baseline values for efficacy parameters will be derived from the daily morning and evening eDiaries and eCRF data collected in the Preintervention Period, specifically the period of time from 14 days before randomization up to the time of randomization.

For the Intervention Period, daily diary day is calculated as (diary date - date of randomization + 1). For the Preintervention Period, daily diary day is calculated as (diary date - date of randomization). However, the day of randomization is study Day 1 regardless. Participants will complete their diary entries twice per day for daily diary.

If a participant withdraws during the Intervention Period, the participant's morning diary assessments of daily eDiary on the day after last dose day will be captured as assessments in the Intervention Period. The impacted Intervention Period week shall be shortened to the end of the

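### The first-dose response endpoints accept every Day 1 evening-diary SBM, so a bowel movement before the in-clinic dose can count as post-dose if it is entered there

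*SAP*

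**What the plan says.** Section 10.3 of both SAPs gives the intent: "A participant is a 24-hour responder if the participant has at least 1 SBM within 24 hours of first dosing of study intervention". The working rule that follows is set in diary entries, not clock time: "Any SBM reported in the evening diary on randomization day and in the morning diary at the day after first dose date" qualifies. The FC SAP adds two related endpoints that the IBS-C SAP lacks. One is an SBM within 48 hours, running from the Day 1 evening diary to the Day 3 morning diary. The other is time to first SBM, measured to the time of the diary report that contains it.

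The evening item (protocol 8.1.1.1, repeated in IBS-C SAP 16.3.4) reads "From when you got up this morning until now, how many times did you poop (and poop came out". Each evening-reported bowel movement is then placed in one of three blocks, the first being "In the morning (from when you woke up until lunch".

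On Day 1 the protocol (10.10.3) says "Participants will be required to complete the eDiary in the clinic for the time period up to immediately prior to randomization". The dose comes later (the fast is in hours): "Administer the first dose of study intervention after completion of all Visit 3 assessments and after confirming the participant has fasted for at least 2". Its date and time are recorded. Section 16.2 of both SAPs assigns the diaries to periods. For baseline, "participants fill out a clinic diary and the assessments in the clinic diary will be part of the Preintervention Period". For treatment, "eDiary assessments in evening diary on the day of randomization will be part of the Intervention Period".

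**The concern.** The evening question, taken literally, opens at waking, several hours before a clinic dose may be given. The rule takes the whole Day 1 evening diary without checking it against the dose time. A child who has a bowel movement at home, reports it in the clinic diary and then answers the evening question as worded will report it twice: once for baseline and once as an apparent response to the drug. Rescue medication is barred from the day before to the day after Visit 3 (protocol 6.5.2), so such a bowel movement would normally qualify as spontaneous.

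In the IBS-C part the 24-hour proportion is presented by dose group with no placebo arm, so false responders add directly to the reported figure. In the FC part the 24- and 48-hour proportions are compared with placebo by a CMH test. False responders in both arms would shrink the difference, and a pre-dose bowel movement would fix time to first SBM at the Day 1 evening report.

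**Working it through.** The plan states no figure for this effect, so the check has two parts.

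**1. The texts side by side**

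- Intent: an SBM after the first dose (section 10.3, both SAPs). Week 1 likewise starts after randomization on Day 1 (section 16.2, both SAPs).
- Rule: any SBM in the Day 1 evening diary counts.
- Recall of that diary: from waking. No Day 1 variant is printed.
- Start of treatment: in the clinic, after all Visit 3 assessments.
- Safeguards looked for: a restart of evening recall after the clinic diary, an instruction to leave out bowel movements already entered, or removal of repeats in the derivation. None appears. Section 16.3.4 counts Day 1 as a half day in each period, which splits the denominator but not the evening count.

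The rule as written can therefore include pre-dose bowel movements. Whether it does depends on what the child enters.

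**2. Size, as an illustration**

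Assumptions, none from the documents except that the rate respects the eligibility limit of fewer than 3 SBMs/week:

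- 2 SBMs/week, Poisson, spread evenly over 16 waking hours;
- dose *h* = 2 to 5 hours after waking;
- the Day 2 morning diary completed on waking;
- every pre-dose bowel movement entered in the evening diary;
- no drug effect.

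| Quantity | Formula | h = 2 | h = 5 |
|---|---|---|---|
| At least one pre-dose bowel movement | 1 − exp(−(2/7) × h/16) | 3.5% | 8.5% |
| 24-hour rule as written (waking to waking) | 1 − exp(−2/7) | 24.9% | 24.9% |
| Post-dose bowel movements only | 1 − exp(−(2/7) × (16 − h)/16) | 22.1% | 17.8% |
| Excess | difference | 2.7 points | 7.0 points |

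The excess is smaller than the pre-dose probability because a child who also has a true post-dose SBM is a responder anyway: 3.5% × (1 − 0.221) = 2.7%, and 8.5% × (1 − 0.178) = 7.0%.

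Varying the inputs (1 to 3 SBMs/week, 15 waking hours, dose 1 to 6 hours after waking) puts the chance of a pre-dose bowel movement between 0.9% and 15.8%. That bounds the false responders from this cause.

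*48-hour endpoint (FC), same assumptions.* Rule: 1 − exp(−4/7) = 43.5%. Post-dose only: 1 − exp(−(2/7) × 30/16) = 41.5% at h = 2, and 1 − exp(−(2/7) × 27/16) = 38.3% at h = 5. The excess is 2.1 to 5.3 points before rounding.

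*FC treatment difference.* If a fraction q of each arm has a pre-dose bowel movement, independent of later response, the responder rate becomes 1 − (1 − q)(1 − p). The between-arm difference is then multiplied by 1 − q: a relative loss of 3.5% to 8.5%.

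*12-week rate.* The expected extra count is (2/7) × 2/16 = 0.036 to (2/7) × 5/16 = 0.089 bowel movements. Over 12 weeks that is 0.003 to 0.007 SBMs/week, against an assumed treatment difference of 1.

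**The case against.** The documents do divide Day 1. The clinic diary covers the time up to randomization, its entries belong to baseline, and participants resume entries later that day. Double counting needs the child to enter again something already reported. The clinic diary's wording is not printed either, so the device prompts and training are not fully visible. This stands: a reader might infer that pre-dose bowel movements do count, but the documents show only that they can.

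A reader might also add the pre-dose hours to a full 24 hours after the dose and conclude that the proportion rises from 24.9% to between 27.5% and 31.3%. The documents do not support that. The window closes at the Day 2 morning diary, so under these assumptions the two diaries together hold one day's bowel movements, which gives 24.9%. With no drug effect this equals the proportion for a true 24-hour window, because the extra hours on Day 1 offset the hours left out on Day 2. That stands as arithmetic. It does not rescue the rule: the hours gained come before the drug and carry no information about it, while the hours lost come after it.

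A tempting remedy is to count only blocks that begin after the dose. That would do harm. With a dose 2 hours and lunch 5 hours after waking (assumed), it would drop three true post-dose hours to remove two pre-dose ones. The proportion would fall to 17.8%, against 22.1% for all post-dose bowel movements.

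Finally, the stakes are low. In IBS-C the endpoint is descriptive and untested; in FC it carries only a nominal p-value and the rule is the same in both arms. Time to first SBM is openly defined by diary report, at roughly 12-hour resolution. All of this stands.

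**Conclusion.** The concern holds as a risk built into the rule. The 24-hour rule in both SAPs, and the 48-hour and time-to-first-SBM rules in the FC SAP only, accept every Day 1 evening-diary SBM although the printed recall begins before the dose. Nothing in the documents prevents a pre-dose bowel movement from being credited to treatment.

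Under the stated assumptions the excess in the 24-hour proportion over post-dose bowel movements is at most about 3 to 7 points. It is an upper figure because it supposes that every pre-dose bowel movement is entered again in the evening; if none is, the excess is zero. It also rests on the assumed rate, waking hours and dose time.

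All the affected measures are 'other' efficacy endpoints. No primary or secondary conclusion changes, and the effect on the 12-week SBM rate is negligible.

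**What to change.** For the 24-hour endpoint in both SAPs, and the 48-hour and time-to-first-SBM endpoints in the FC SAP:

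1. Do not count a Day 1 evening-diary bowel movement whose reported time block ended before the recorded first-dose time. The blocks are bounded by meals, so the SAP should state the clock times used for lunch and dinner.
2. Keep bowel movements in the same block as the dose in the main count. Add a sensitivity count that removes as many of them as were already reported since waking in the Day 1 clinic diary.
3. If the device restarts Day 1 evening recall after the clinic diary, state that instead; steps 1 and 2 are then unnecessary.

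Leave the Week 1 and 12-week SBM rates unchanged.

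The cost is a short derivation rule and one extra count, using data already collected. The limit is that same-block bowel movements remain partly ambiguous. For a dose before lunch, step 1 removes nothing, because the morning block runs to lunch, and the sensitivity count carries the correction.
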